10.2 DEFINITION OF BASELINE, STUDY VISITS, AND VISIT WINDOWS

The last non-missing assessment made prior to the first dose of study drug will be used as the baseline value. The data will be analyzed according to the visits recorded in the eCRF.

10.3 HANDLING OF MISSING DATA

Rules for handling of missing attributes of adverse events are specified in section 10.8.2. Rules for dates imputations are defined below.

10.3.1 DATES IMPUTATIONS

The rules below will be used for classification of AEs as treatment-emergent and medications as concomitant or prior. Data will be presented in the data listings as collected on the eCRF.

The following rules will be applied for AEs and medications with incomplete start dates:

- If partial start date is equal to the corresponding part of the treatment start date then consider the start date equal to the treatment start date,
- If day is missing for start date and month and year are not the same as month and year for the first treatment date, then impute day 1 of the month,
- If day and month are missing for start date and the year is not the same as year for the first treatment date, then impute January 1st of the year.

The following rules will be applied for AEs and medications with incomplete end dates:

- If day is missing for end date and month and year are non-missing, then day will be imputed as last day of the month,
- If day and month are missing for end date and year is non-missing, then day and month will be imputed as December 31st.

AEs and medications without any start and end date information will not be imputed.

The following rules will be applied for incomplete diagnosis date/date of first treatment for bleeding episode:

- If day is missing then impute day 1 of the month
- If day and month are missing then impute January 1st of the year.

10.4 PATIENT DISPOSITION

Subject disposition will be summarized separately for each phase of the study.

The number of subjects screened and reasons for screen failure, will be summarized in the screened population.

The number and percentage of subjects enrolled, completing the study along with reasons for study discontinuation, and number of subjects in each population will be summarized in the Safety population. The number and percentage of subjects who complete 50 ED Visit (Treatment Phase), 100 ED Visit (Continuation Phase) will be summarized in each population and overall.

A listing of study disposition data will be produced.

10.5 PROTOCOL DEVIATIONS

The number and percentage of subjects with at least one major protocol deviation and the categories of the major protocol deviations will be summarized in the Safety population.

Protocol deviations will be classified to major and minor as specified in the Protocol Deviations Management Plan.

All protocol deviations will be provided in a listing.

10.6 PATIENT CHARACTERISTICS

10.6.1 BASELINE AND DEMOGRAPHIC CHARACTERISTICS

Descriptive statistics for continuous variables (age at informed consent [years], height [cm],

weight [kg], and body mass index [kg/m²]) and frequency counts and percentages for categorical demographic variables (gender, categorized age (<2 years, 2 - <=11 years), race, and ethnicity) will be summarized in the Safety population.

Age at informed consent (years) will be calculated as (informed consent date–date of birth)/365.25.

Baseline and demographics characteristics will be provided in a listing.

10.6.2 MEDICAL HISTORY AND CURRENT MEDICAL CONDITIONS

Disease characteristics will be summarized in the Safety population, and will include descriptive statistics for

- age at hemophilia diagnosis (years)
- time since diagnosis date (months), calculated as (informed consent date – diagnosis date+1)/30.4375;
- time from date first treated for bleeding episode (months), calculated as (informed consent date–date first treated for bleeding episode date+1)/30.4375;
- total number of ED of factor IX replacement therapy

and frequency counts and percentages for:

- severity;
- whether factor IX mutation known (yes/no);
- type of factor IX mutation;
- target joints/body areas;
- swelling (yes/no) and level;
- muscle atrophy (yes/no) and level;
- loss of range of motion (yes/no);
- pronation, supination, flexion, plantar flexion and dorsiflexion levels;
- flexion contracture (yes/no) and level.

Bleeding history will be summarized in Safety population and will include:

- number of bleeding episodes during 6 months prior to screening;
- percentage of spontaneous bleeding episodes;
- number of infusions needed to control the bleeding episode.

If bleeding history is not documented, then estimations provided in the eCRF will be summarized.

Medical history will be summarized in the Safety population and will be coded using the latest version of Medical Dictionary for Regulatory Activities (MedDRA) classification and summarized by System Organ Class (SOC), preferred term (PT) and severity grade at screening. Subjects having the same medical condition (based on SOC, PT, and severity grade) more than once will be counted only once for a particular SOC, PT, and severity grade.

All medical history will be listed including medical history itself, hemophilia B history, and bleeding history.

10.6.3 PRIOR AND CONCOMITANT MEDICATIONS

All prior and concomitant medications will be coded using the latest version of World Health Organization Drug Dictionary.

The number and percentages of subjects with at least one prior non-study factor IX therapy and prior medications will be summarized by Anatomical Therapeutic Chemical (ATC) level 4 and ATC level 2 class.

The number and percentages of subjects with at least one concomitant medication will be summarized by ATC level 4 and ATC level 2 class.

Prior and concomitant medications will be summarized in the Safety population.

Subjects receiving the same medication more than once will be counted only once for a particular medication class. A medication is considered prior if the end date of the medication is prior to the first study drug dose date. A medication is considered concomitant if it is administered after the first study drug administration. Imputation rules specified in Section 10.3 will be applied to partial/missing dates.

Medications having both start and end dates missing will be considered concomitant; in the case of a missing start date and not missing end date the medication will be considered concomitant, unless the end date is prior to the date of the first dose.

All prior and concomitant medications will be provided in a listing.

10.6.4 CONCOMITANT PROCEDURES

All concomitant procedures will be coded using the latest version of MedDRA classification. A procedure is considered concomitant if performed after the first study drug administration.

All concomitant procedures will be provided in a listing.

10.7 EFFICACY ENDPOINTS AND ANALYSIS

Efficacy data will be analyzed in the Safety population. Descriptive summaries and listings of all Treatment and Continuation Phase efficacy endpoints as described in section 10.7.2, as well as the surgeon's assessment of estimated blood loss during and after surgery, will be provided. The efficacy endpoints are summarized for each study phase (Treatment and Continuation) and combining data across study phases.

10.7.1 ANALYSIS OF PRIMARY EFFICACY ENDPOINT

The number of bleeding episodes and the number of months observed will be determined from the subject diary. The months of observation will be calculated from the first date of the Treatment Phase to the last prophylaxis entry into the subject diary.

ABR while on prophylaxis to prevent bleeding episodes will be calculated and summarized using median, Q1, Q3 and 95% exact confidence interval for the mean, assuming that the rates follow a Poisson distribution.

ABR overall = (number of bleeding episodes starting from first dose after PK Phase up to 3 days after the last dose of APVO101 given for prophylaxis)/[(treatment end date +3 – treatment start date+1)/365.25]. If a subject left the study earlier than 3 days after last dose, date of end of study will be taken instead of (treatment end date +3 days).

ABR Treatment Phase = (number of bleeding episodes starting from first dose after PK Phase up to 3 days after the last dose of APVO101 given for prophylaxis up to 50 ED)/[(last dose ≤50ED +3 – treatment start date +1)/365.25]. In case first dose after 50 ED occurred earlier than 3 days after 50 ED then this dose date – 1 should be taken as reference end date. If a subject left the study earlier than 3 days after last dose in treatment phase, date of end of study will be taken instead of (last dose ≤50 ED + 3 days).

ABR Continuation Phase = (number of bleeding episodes starting from first dose after 50 ED up to 3 days after last dose of APVO101 given for prophylaxis)/[(treatment end date +3 – first dose after 50 ED+1)/365.25]. If a subject left the study earlier than 3 days after last dose, date of end of study will be taken instead of (treatment end date +3 days).

Note: a bleeding episode which occurred after PK dose but prior to completion of PK assessment will be included into ABR calculations.

In addition, analysis of ABR will be repeated on the normalized data (square-root transformation will be used to normalize ABR).

Number of subjects with at least one bleeding episode and no bleeding episodes will also be summarized.

The analysis of ABR will be repeated for Spontaneous ABR which will consider only spontaneous bleeding episodes in the numerator. Denominator will remain the same as for ABR. Spontaneous ABR for Treatment, Continuation phases as well as overall will be derived.

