5. STUDY DESCRIPTION

5.1 STUDY DESIGN AND TREATMENT

Study APVO101-903 is a Phase 3/4, single arm, open-label clinical trial. The purpose of the study is to evaluate PK, safety, and efficacy of APVO101 prophylaxis in severe or moderately severe hemophilia B subjects <12 years of age. The study is designed to gather information in 2 age groups of previously treated (with a minimum of 50 previous ED to factor IX replacement therapy) pediatric subjects, specifically those <6 years of age and 6-12 years of age.

Study APVO101-903 consists of 3 distinct phases:

- PK Phase
- Treatment Phase (from first dose after PK phase and up to 50 ED visit)
- Continuation Phase (starting from first dose after 50 ED visit)

Up to 22 subjects will be enrolled in order to have 15 and 20 evaluable subjects to complete the study (i.e., completion of PK assessments and a minimum of 50 ED visit). Treatment with APVO101 to support a surgical procedure (if required) is permitted for subjects in Treatment/Continuation phases of the study.

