12. DEVIATIONS FROM ANALYSIS AS DESCRIBED IN THE PROTOCOL

Protocol version 3.0 amendment 2.0 section 11.4.2. 'Efficacy analysis specifies:

The annualized bleeding rate will be calculated and summarized, including the median, interquartile range and the 95% exact confidence interval for the median, assuming that the rates follow a Poisson distribution.

Sponsor confirmed that the wrong word has been used in this statement due to oversight. 95% confidence intervals are planned to be derived for mean (not median), analyzed in the same manner as the previous IB1001 studies.

Additional analysis of normalized (square-root transformed) ABR was also added to the efficacy

analysis to provide data comparable to results from studies IB1001-01 and IB1001-02.

According to the protocol, efficacy endpoints are evaluated for the Treatment and Continuation phases of the study (section 11.2.2). The Treatment phase begins after PK phase assessments are completed (section 5.7). The sponsor clarified that the evaluation of APVO101 efficacy with respect to prevention of breakthrough bleeding and with respect to control of hemorrhaging in pediatric patients, should be assessed after the initial infusion of APVO101 (PK phase) as this first infusion of 75 IU/kg is intended to protect subjects prophylactically. Therefore, any bleeding episode that occurs during the PK phase, will be evaluated and considered as belonging to the Treatment phase.

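### SAP 10.7.1 gives no single start date for the primary ABR: the numerator formulas start after the PK Phase, the Note and Section 12 count bleeds from the PK infusion, and the denominator's start is undefined

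*SAP*

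**What the plan says.** SAP Section 10.7.1 gives three ABR formulas.

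- **Overall and Treatment Phase.** Both numerators take the "number of bleeding episodes starting from first dose after PK Phase". Both denominators subtract a *treatment start date*. Spontaneous ABR uses the same denominators.
- **Continuation Phase.** The numerator is the "number of bleeding episodes starting from first dose after 50 ED up to 3 days after last dose of APVO101 given for prophylaxis", and the denominator starts at that same dose.

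The section also says: "The months of observation will be calculated from the first date of the Treatment Phase to the last prophylaxis entry into the subject diary". Its Note then adds that "a bleeding episode which occurred after PK dose but prior to completion of PK assessment will be included into ABR calculations". Section 10.7.2 repeats the Note.

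Section 12 explains the Note. The sponsor's position is that efficacy "should be assessed after the initial infusion of APVO101 (PK phase) as this first infusion of 75 IU/kg is intended to protect subjects prophylactically", so that "any bleeding episode that occurs during the PK phase, will be evaluated and considered as belonging to the Treatment phase".

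*Treatment start date* is not defined in SAP Section 2 or elsewhere in the SAP text available for review.

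**The concern.** Under the formulas as written, a bleed between the PK infusion and the next dose falls before the numerator begins. Under the Note and Section 12 it counts. The formulas were not updated when the sponsor's clarification was added.

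The denominator is the more open part, because the SAP supports two start dates. On one of them, events are counted over time that is left out of the person-time. On the other, two sentences in 10.7.1 are wrong. Two programmers could each follow the text and obtain different overall, Treatment-Phase and spontaneous ABRs for the primary efficacy endpoint.

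**Working it through.** **1. The two readings of *treatment start date*.**

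| Reading | Support in the SAP | Consequence |
|---|---|---|
| First post-PK dose | Section 5.1: "Treatment Phase (from first dose after PK phase and up to 50 ED visit"; 10.7.1, months of observation from the start of the Treatment Phase | PK-phase bleeds are in the numerator, their time is not in the denominator |
| PK infusion | 10.3.1 uses the term in rules introduced by "The rules below will be used for classification of AEs as treatment-emergent and medications as concomitant or prior"; 10.8.2 ties treatment-emergent to the first study drug administration, which is the PK infusion; Section 12 assesses efficacy after that infusion | Numerator and denominator match, but the formula wording and the months-of-observation sentence do not fit |

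Either way some text in 10.7.1 has to change.

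**2. Treatment-Phase length.** The plan's own figure is 50 exposure days (ED), about 6 months. At two infusions a week, 50/2 × 7 = 175 days, and 175/30.4375 = 5.75 months, which agrees. SAP Section 2 counts the PK infusion as an ED, which leaves 49 post-PK doses. I also show 50. With doses 3.5 days apart on average and the formula's +3 and +1 days:

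- 49 doses: 48 × 3.5 + 4 = 172 days
- 50 doses: 49 × 3.5 + 4 = 175.5 days

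**3. Effect of the start date on the denominator.** The gap from PK infusion to first prophylaxis dose is not given. PK sampling ends at 46–50 hours, so I assume 2 to 7 days.

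- Shortest gap: 2/175.5 = 1.1%; 2/172 = 1.2%
- Longest gap: 7/175.5 = 4.0%; 7/172 = 4.1%

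For overall ABR at 100 ED (98 × 3.5 + 4 = 347 days), the change is 2/347 = 0.6% to 7/347 = 2.0%.

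**4. One subject whose only bleed is in the PK Phase (Treatment-Phase ABR, 172 days).**

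- Formula wording alone, without the Note: 0
- Note, clock from the first post-PK dose: 365.25/172 = 2.12
- Note, clock from the PK infusion: 365.25/174 = 2.10 (2-day gap) to 365.25/179 = 2.04 (7-day gap)

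**5. Group rate, 20 subjects with equal follow-up.** Person-years are 20 × 172/365.25 = 9.42 from the first post-PK dose. From the PK infusion they are 20 × 175/365.25 = 9.58 with a 3-day gap. The totals of 3 and 14 other bleeds are illustrative and give rates near the earlier medians of 0.3 and 1.52. One PK-phase bleed is added to each. The intervals are exact Poisson 95% intervals.

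| Bleeds | Clock from first post-PK dose | Clock from PK infusion |
|---|---|---|
| 3 + 1 | 0.42 (0.12–1.09) | 0.42 (0.11–1.07) |
| 14 + 1 | 1.59 (0.89–2.63) | 1.57 (0.88–2.58) |

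With a 7-day gap (20 × 179/365.25 = 9.80 person-years) the rates on the PK-infusion clock are 4/9.80 = 0.41 and 15/9.80 = 1.53.

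**6. How many PK-phase bleeds to expect.** Protocol Section 1.2.2 gives median ABRs of 0.3 (earlier pediatric study) and 1.52 (earlier study, mostly adolescents and adults, on prophylaxis). Using these as rates is an assumption.

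- Low: 22 × (50/24)/365.25 × 0.3 = 0.04
- High, taking the window as 3 calendar days: 22 × 3/365.25 × 1.52 = 0.27

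**The case against.** The best defence is that 10.7.1 states a rule and then an explicit exception, and that Section 12 documents the reason. That stands for the numerator: the intent is to count PK-phase bleeds, and only the formula wording lags behind. It does not settle the denominator, because neither the Note nor Section 12 says when person-time begins. The Continuation-Phase formula, with one start in both parts, shows what is missing.

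It is also fair to say that the analysis is descriptive, that the effect is small, and that any bias on the first reading raises the ABR and so runs against the product. The rating reflects this.

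A reader might infer more than the documents support:

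- *That a bleed between the last PK sample and the first prophylaxis dose is neither in nor out.* Section 12 says that the Treatment Phase begins once PK assessments are complete, which places such a bleed in that phase. Under Section 5.1 it is still in the PK Phase, and Section 12 counts it there. It counts on both readings; only the formula wording omits it.
- *That the two candidate dates are only the 50-hour PK window apart.* The documents do not give the gap, so it has to be an assumed range.
- *That the effect is confined to the rare subject with a PK-phase bleed.* The start date rescales every non-zero overall and Treatment-Phase ABR. Conversely, subjects with no counted bleeds have an ABR of zero on either date.
- *That a treated bleed during the PK window leads to a second PK infusion and a much longer gap.* Protocol Section 5.7.3 says only that the washout restarts. A repeat infusion is an inference.

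**Conclusion.** The inconsistency is real and minor. It affects overall, Treatment-Phase and the matching spontaneous ABR, not Continuation-Phase ABR. The numerator's intent is settled by Section 12; the numerator's wording and the denominator's start are not.

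The choice of start date moves the Treatment-Phase denominator by about 1 to 4%, assuming a 2 to 7 day gap and twice-weekly dosing. Fewer than 0.3 PK-phase bleeds are expected in 22 subjects, assuming that the earlier median ABRs serve as rates. No conclusion of this descriptive trial is likely to turn on it. What is at stake is that the primary efficacy endpoint can be reproduced from its written definition. Some pages were removed from the public text, so a definition there cannot be wholly excluded, but it would not mend the conflict between the formula wording and the Note.

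**What to change.** In line with Section 12, define *treatment start date* for ABR as the date of the first PK infusion. Then, in Section 10.7.1:

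- use that date in both numerator and denominator of the overall, Treatment-Phase and corresponding spontaneous ABR;
- count every bleed from that date, including any between the end of PK assessments and the first prophylaxis dose;
- reword the two numerators and the months-of-observation sentence to agree. That sentence should also end where the formulas do: it now stops at the last prophylaxis diary entry, while they run to 3 days after the last dose.

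A sensitivity summary that starts both parts at the first post-PK dose is optional.

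The cost is a few lines of SAP text. The dates come from infusion records already collected, and nothing changes for subjects or sites.

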10.7.2 ANALYSIS OF SECONDARY EFFICACY ENDPOINTS

Both types of secondary efficacy endpoints (bleeding episode level and subject level) will be presented descriptively for the Treatment Phase (bleeding episodes and subject level assessments occurred from first dose to 50 ED up to 3 days after last dose of APVO101 given for prophylaxis), Continuation Phase (bleeding episodes and subject level assessments occurred on or after first dose after 50 ED given for prophylaxis) and overall (all bleeding episodes and subject level assessments in a subject).

Summaries for bleeding episode level endpoints will include:

- Number and percentage of bleeding episodes within each category of subject's rating of efficacy;
- Number and percentage of bleeding episodes within each category reported by subjects as answer to question "How long did it take for the pain to stop?"
- Number and percentage of bleeding episodes within each category of highest level of pain during the bleeding episode.
- Number and percentage of bleeding episodes within each category reported by subjects as answer to question "How long did it take for the swelling to go down?"
- Descriptive statistics for time from onset of bleeding to the first infusion (minutes) as continuous variable

- Descriptive statistics for time from onset of treatment until resolution of the bleeding episode (minutes) as continuous variable
- Descriptive statistics for number of infusions required to treat the bleeding episode as continuous and categorical variable

Note: a bleeding episode which occurred after PK dose but prior to completion of PK assessment will be included into ABR calculations.

Summaries for subject level endpoints will include by-visit summaries for the following Investigator's assessments:

- APVO101 prophylaxis efficacy assessment
- Efficacy for control of bleeding episodes assessment

All data for subject assessments of bleeding episodes and Investigator assessments of efficacy will be listed.

10.7.3 ANALYSIS OF EXPLORATORY EFFICACY ENDPOINTS:

The following endpoints related to surgery will be summarized as frequency variables:

- Pre- and Post-surgery assessments:
 - Surgeon's assessment of total blood loss
- 12 hours (± 3 hours) post-surgery assessment and 24 hours (± 3 hours) post-surgery assessment:
 - Surgeon's assessment of total blood loss
 - Surgeon's assessment of APVO101 hemostatic efficacy

All data related to surgeries will be listed including reasons for procedures, prior and post-surgery assessments.

Vital signs collected during surgery will be listed.

10.8 SAFETY ENDPOINTS AND ANALYSIS

All safety outcomes will be analyzed in the Safety population.

Safety will be evaluated by presenting summaries of exposure to study treatment, AEs, physical examination, vital signs, local laboratory evaluations (hematology, serum chemistry, and urinalysis) and central laboratory evaluations (inhibitory factor IX antibodies, non-inhibitory factor IX binding antibodies, anti-CHOP antibodies, and thrombogenic markers).

10.8.1 EXPOSURE TO STUDY TREATMENT AND COMPLIANCE

Exposure and compliance parameters will be summarized descriptively. Parameters to be summarized are specified in section 2.

In addition, number and percentage of subjects who fall under the following categories (not mutually exclusive) of treatment exposure will be presented:

- Subjects with ≥ 50 ED
- Subjects with ≥ 100 ED
- Subjects with ≥ 150 ED
- Subjects with ≥ 200 ED

Number of surgeries overall and per subject, number of infusions due to surgeries overall and per surgery, and total dose administered per surgery will be calculated by treatment regimen (bolus vs. continuous infusion); subjects may receive both bolus and continuous infusions and, in such cases, will be included in the summaries for both treatment regimens. For subjects treated with bolus infusion, the number of bolus infusions, average APVO101 dose (IU/kg), and total APVO101 exposure (IU) will be presented by surgery visit (pre-surgery and post-surgery) and overall. For subjects treated with continuous infusion, the average APVO101 dose (IU/kg/hr) and total APVO101 exposure (IU) will be presented.

Compliance derivation algorithm is provided in section 2. Compliance will be summarized as continuous variable as well as categorized into $\geq 80\%$, $< 80\%$. Reasons for dose/frequency modifications will also be tabulated.

Summaries described in this section will be done separately for Treatment/Continuation Phases combined, surgeries and overall, except for compliance and reasons for dose/frequency modifications which will be presented for all study duration.

A by-subject listing with the treatment administration data will be presented. In addition, a listing of all derived parameters will be produced, and it will include total value of exposure (IU) and exposure days per study.

Dose regimen data together with reasons for changes in dose regimen will be listed.

